1.2.4 Biological versus standard optimization algorithms

Radiation treatment planning for intensity modulated radiation therapy typically uses inverse planning algorithms, whereby the physician defines dose limits to organs at risk of injury and defines the dose goals to the target. The computer then iteratively optimizes the radiation delivery such that it attempts to reach the dose goal to the target while respecting the organ at risk (normal tissue) dose constraints. A number of dose limits have been published for normal tissues and, in general, these are often adapted from those included on randomized trials or from the QUANTEC project [32]. Biological optimization uses biological modeling to incorporate local tumor control probability data (TCP) and normal tissue complication probability data (NTCP) into the planning process. This approach requires integration of TCP and NTCP data into the treatment planning process. Although patients will be treated using standard planning techniques, we will explore the capacity of this process to alter radiation treatment planning retrospectively from the imaging datasets obtained on this trial.

1.2.5 Summary

The goal of this study is to evaluate a new regimen that would reduce the duration of treatment compared to the current standard. For patients with no evidence of tumor on clinical evaluation (imaging or biopsy as clinically indicated) this would be accomplished by increasing the fraction size to the prostate bed to allow for more rapid treatment. Because the dose is delivered more rapidly, the total dose would be adjusted for biological equivalence to tumor when compared to standard fractionation. Thus, an equivalent biological dose would be delivered to the tumor bed more rapidly than the current standard. We anticipate that this approach will be tolerable as newer technologies have provided the capacity to enhance the conformality of dose around the target. In addition, daily imaging guidance allows increased confidence that normal tissue is maximally spared and tumor tissue is included. This approach has begun to be explored with conservative increases in fraction size (2.2 - 2.5 Gy) and appears safe [33-38]. In patients with no visible tumor, our study aims to accelerate using the most modern techniques, with daily image guidance, and with consideration of not only toxicity, but Quality of Life (QoL).

In patients with tumor identified on imaging studies or on clinical biopsy, we aim to reduce the dose delivered to the prostate bed to a level considered adequate of sterilizing microscopic disease and escalate dose to the areas of known recurrence. In general, the site of local recurrence after prostatectomy has historically not been known after prostatectomy based on limitations with imaging in the post-prostatectomy setting. Occasionally, an area would be palpated in the bed on digital rectal examination, but often not until the PSA was higher than what is traditionally used as a cut off for delivering radiation treatments. Historically, MRI was not performed and CT imaging gave poor soft tissue contrast in this anatomic location. More recently, it has become clear that recurrences can often be identified with high quality MR imaging using an endorectal coil or advanced imaging techniques, and in many cases these areas are biopsied for confirmation [39, 40]. Because the site of recurrence is known, this provides the opportunity in this patient subset to escalate dose to the recurrent disease while reducing the dose to the prostate bed.

Collectively, these approaches are evaluating the tolerability of more rapidly delivering radiation and reducing normal tissue exposure through the use of highly conformal radiation treatments.

2 ELIGIBILITY ASSESSMENT AND ENROLLMENT

2.1 ELIGIBILITY CRITERIA

2.1.1 Inclusion Criteria

2.1.1.1 Patients must have histologically or cytologically confirmed adenocarcinoma of the prostate.

2.1.1.2 Indications for post-prostatectomy radiation exist:

- Disease progression (detectable PSA on two measurements obtained at least one month apart) or
- indications for adjuvant radiation exist (if undetectable PSA): pathologic T3, T4, N+ disease or positive margins (within 1 year of prostatectomy).

2.1.1.3 Age \geq 18 years.

Abbreviated Title: Image guided radiation

Version Date: 06/03/2024

2.1.1.4 ECOG performance status ≤ 1 (Karnofsky $\geq 60\%$, see [Appendix A](#))

2.1.1.5 Ability of subject to understand and the willingness to sign a written informed consent document.

2.1.1.6 Radiation is teratogenic; thus, men must agree to use adequate contraception (hormonal or barrier method of birth control; abstinence) prior to study entry, for the duration of study participation and up to 120 days after the last radiation. Should a woman become pregnant or suspect she is pregnant while her partner is participating in this study, she should inform her treating physician immediately.

2.1.1.7 HIV positive patients are included if CD4+ T-cell count > 200 cells/uL; on stable antiretroviral therapy for > 1 year with HIV viral load < 200 copies/mL, and no history of opportunistic infections in > 1 year.

2.1.2 Exclusion Criteria

2.1.2.1 Patients who are receiving any other investigational agents concurrently.

2.1.2.2 Documented metastases of prostate cancer outside of the pelvis (pelvic lymph nodes are allowed only if within the prostate bed region).

2.1.2.3 History of radiation that would overlap with the intended treatment to the prostate bed.

2.1.2.4 Known contraindications to radiation such as inflammatory bowel disease, active systemic lupus or scleroderma, or radiation hypersensitivity syndrome (Ataxia Telangiectasia or Fanconi's Anemia)

2.1.2.5 Subjects with any coexisting medical or psychiatric condition which, in the opinion of the Investigator likely to interfere with study procedures and/or results.

2.1.2.6 Medically indicated use of known radiosensitizing drugs (such as protease inhibitors)

2.1.3 Recruitment Strategies

Participants will be identified from [name] referral base, largely via referrals from the Urologic Oncology Branch, via the multi-disciplinary clinic, and via direct outside referrals to [name] clinic. [name] has developed an excellent professional relationship with numerous referring physicians in the surrounding area who refer patients.

This protocol may be abstracted into a plain language announcement posted on NIH websites and on NIH social media platforms.

2.2 SCREENING EVALUATION

Screening evaluation testing/procedures are conducted under the separate screening protocol, 01-C-0129 (Eligibility Screening and Tissue Procurement for the NIH Intramural Research Program Clinical Protocols). Assessments performed at outside facilities or on another NIH protocol within the timeframes below may also be used to determine eligibility once a patient has signed the consent.

Within 4 weeks prior to enrollment unless otherwise noted below:

- Physical Evaluation: Complete medical history and physical examination, including vital signs and ECOG performance status.
- Laboratory Evaluations

Abbreviated Title: Image guided radiation

Version Date: 06/03/2024

- HIV Viral serology and HIV viral load
- CD4+ T-cell count for HIV positive patients
- PSA
- Radiographic Evaluations (within 4 months prior to enrollment):
 - multiparametric MRI (mpMRI) of the prostate bed
 - CT of the abdomen and pelvis (with oral and IV contrast) may also be obtained for evaluation of eligibility, particularly if MRI is not felt to adequately have staged the pelvic and abdominal lymph nodes
 - whole body bone scan or 18F NaF PET if felt to be required by the clinician; this imaging is not required if MRI and/or CT scans adequately staged the pelvic and abdominal lymph nodes, or if other standard scans were performed (e.g., 18F-DCFPyL) that confirm the disease status
- Histological or cytological pathology documentation, confirming adenocarcinoma of the prostate and for determination of whether indication for adjuvant radiation exists.
- Collection of medical records pertaining to medical history as well as testing and procedures for the diagnosis under study (e.g., imaging results including 18F-DCFPyL PET/CT)

2.3 PARTICIPANT REGISTRATION AND STATUS UPDATE PROCEDURES

Registration and status updates (e.g. when a participant is taken off protocol therapy and when a participant is taken off-study) will take place per CCR SOP ADCR-2, CCR Participant Registration & Status Updates found at <https://ccrod.cancer.gov/confluence/pages/viewpage.action?pageId=73203825>.

2.4 TREATMENT ASSIGNMENT PROCEDURES

Cohorts

Number	Name	Description
1	Recurrent tumor visible	Recurrent tumor visible
2	Recurrent tumor NOT visible	Recurrent tumor NOT visible

Arms

Number	Name	Description
Arm 1	Prostate bed with integrated boost	Radiation will be delivered to an escalated dose to areas of recurrent prostate cancer identified on imaging and a reduced dose will be delivered to the entire prostate bed.
Arm 2	Prostate bed irradiation only	Radiation will be delivered to the prostate bed only

Arm Assignment

Patients in Cohort 1 will be directly assigned to Arm 1. Patients in Cohort 2 will be directly assigned to Arm 2.

2.5 BASELINE EVALUATION

Tests done at screening do not need to be repeated on baseline if performed in designated time frame prior to start of treatment:

Within 2 weeks prior to treatment initiation:

- Clinical assessment with attention to any new medications or interventions since screening history and physical examination including vital signs and ECOG performance status.
- Hematological profile: CBC with differential and platelet count,
- Lymphocyte phenotype TBNK
- Biochemical profile: electrolytes, creatinine, BUN, alkaline phosphatase, ALT, AST, total and direct bilirubin,
- PSA, testosterone,
- Questionnaires: Expanded Prostate Cancer Index Composite (EPIC-26), SHIM, AUA-SI, PROMIS Depression SF4a, PROMIS Anxiety SF4a, PROMIS Psychological Impact Positive SF 4a, Decision Regret Scale. For English speaking patients only.
- Collection of blood and urine for correlative assays (see section **5.1** for further details).
- If available, tissue blocks or sections from prostatectomy or biopsies will be requested

Within 4 months prior to treatment:

- Radiographic evaluation: Multiparametric MRI of the prostate bed.

3 STUDY IMPLEMENTATION

3.1 STUDY DESIGN

There will be two Arms in this trial. Arm 1 includes patients with rising PSA after prostatectomy for whom recurrent tumor has been visualized in the pelvis, providing a target for dose escalation. Arm 2 includes patients with rising PSA with no visualized tumor on imaging or patients with indications for adjuvant radiation after prostatectomy. Patients in whom MRI is contraindicated may enroll on Arm 2 if no evidence of disease is noted on other imaging modalities.

In Arm 1 radiation will be delivered to an escalated dose to areas of recurrent prostate cancer identified on imaging and a reduced dose will be delivered to the entire prostate bed.

In Arm 2 radiation will be delivered to the prostate bed only in patients for whom no recurrent tumor is visualized on imaging or if MRI imaging was contraindicated.

On Dose Level 1 treatments will be delivered in 20 fractions (approximately 4 weeks), on Dose Level 2 - in 15 fractions (approximately 3 weeks), on Dose Level 3 - in 10 fractions (approximately 2 weeks).

Abbreviated Title: Image guided radiation

Version Date: 06/03/2024

Treatment will be administered in daily fractions Monday through Friday except in the case of machine malfunction or federal holiday.

Daily image guidance with cone beam CT will be preferred. kV/kV imaging is allowed if the Cone beam CT imager is unavailable. An additional post-treatment cone beam CT after each fraction may be obtained to assess intrafraction motion.

Table 1 Fraction Dose Escalation Schedule

	Cohort 1, Arm1: Recurrent tumor visible, prostate bed with integrated boost		Cohort 2, Arm 2: Recurrent tumor NOT visible, prostate bed irradiation only	
Dose level	Dose to prostate bed	Dose to tumor	Dose to prostate bed	Dose to tumor
Level 1: 20 fractions	45.8 Gy in 2.29 Gy fractions	60.4 Gy in 3.02 Gy fractions	56.4 Gy in 2.82 Gy fractions	-
Level 2: 15 fractions	41.85 Gy in 2.79 Gy fractions	54.6 Gy in 3.64 Gy fractions	51.2 Gy in 3.41 Gy fractions	-
Level 3: 10 fractions	36.4 Gy in 3.64 Gy fractions	47.1 Gy in 4.71 Gy fractions	44.2 Gy in 4.42 Gy fractions	-

Serial PSA and serial correlative studies will be collected for two years post-treatment.

3.1.1 Dose Limiting Toxicity

The DLT period includes treatment period (4, 3 or 2 weeks depending on Dose Level) and the 3 following weeks. DLT is defined as any of the following:

- Grade 3 rectal, small bowel, or urinary toxicity that does not resolve to Grade 2 or less within 4 days with appropriate medical management.
- Other grade 3 in-field toxicities attributable to RT that do not resolve to Grade 2 or less within 4 days with medical management.
- Delays of more than one week in completing radiation treatment due to toxicity (cumulative duration of delay over the course of the entire treatment).

Additionally, toxicities that occur more than 3 weeks after completion of treatment and during the 24 month follow up period will be followed and scored but will not be used for escalation with the following exception. If Grade ≥ 4 late bowel or bladder injury is observed in 2 patients at any Dose level, dose escalation will be terminated and the dose below that dose level in which the toxicity was observed will be considered the MTD. Early and late toxicities used for assessment of DLTs should be attributable (possible, probable or definite) to radiation. Changes in sexual and erectile function will not be considered a DLT. MTD will be determined for each Arm separately.

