If a patient did not experience DLT and did not finish treatment, he will not be evaluable for toxicity and will be replaced in the dose level.

If patients develop side effects considered DLT, they will be taken off protocol treatment and may receive additional radiation as needed in standard fractionation to complete the treatment.

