3.7.1 Criteria for removal from protocol therapy

- Completion of protocol therapy
- Participant requests to be withdrawn from active therapy
- Unacceptable Toxicity as defined in section [3.1.1](#)
- PI discretion

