6 DATA COLLECTION AND EVALUATION

6.1 DATA COLLECTION

The PI will be responsible for overseeing entry of data into a 21 CFR Part 11-compliant data capture system provided by the NCI CCR and ensuring data accuracy, consistency and timeliness. The principal investigator, associate investigators/research nurses and/or a contracted

Abbreviated Title: Image guided radiation

Version Date: 06/03/2024

data manager will assist with the data management efforts. Primary and final analyzed data will have identifiers so that research data can be attributed to an individual human subject participant.

All adverse events, including clinically significant abnormal findings on laboratory evaluations, regardless of severity, will be followed until return to baseline or stabilization of event. Document AEs from the first study intervention through at least 30 days after the last study treatment administration. Beyond 30 days after the last study treatment administration, only adverse events which are serious and related to the study intervention need to be recorded.

An abnormal laboratory value will be considered an AE if the laboratory abnormality is characterized by any of the following:

- Results in discontinuation from the study (except for a rising serum PSA)
- Is associated with clinical signs or symptoms
- Requires treatment or any other therapeutic intervention
- Is associated with death or another serious adverse event, including hospitalization.
- Is judged by the Investigator to be of significant clinical impact
- If any abnormal laboratory result is considered clinically significant, the investigator will provide details about the action taken with respect to the test drug and about the patient's outcome.

End of study procedures: Data will be stored according to HHS, FDA regulations, and NIH Intramural Records Retention Schedule as applicable.

Loss or destruction of data: Should we become aware that a major breach in our plan to protect subject confidentiality and trial data has occurred, this will be reported expeditiously per requirements in section [7.2.1](#).

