8.4 STATISTICAL ANALYSES

8.4.1 General Approach

This is a phase I study. There are two arms to this study for 1) patients with prior prostatectomy, rising PSA, and visible tumor on imaging, and 2) patients with prior prostatectomy with no visible tumor on imaging (rising PSA or indications for adjuvant treatment). Arms are enrolled and escalated separately. Dose level groups of 3-6 patients are evaluated at each dose level. The dose level on which 2 patients experience unacceptable toxicity is considered to have exceeded the MTD. The next lower dose level on which no more than 1/6 patients experience unacceptable toxicity is considered the MTD for each arm of the study.

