8.4.4 Safety Analyses

Adverse events will be coded as per the CTCAE v4.0. Each AE will be coded once for each patient based on the maximum severity during the assessment period. The relationship of AEs to study intervention will be recorded in addition to the onset date, end date, severity, expectedness, and outcome.

Dose-limiting toxicities are defined as follows (during treatment and within the first three weeks after treatment):

- Grade 3 rectal, small bowel, or urinary toxicity that does not resolve to Grade 2 or less within 4 days with medical management
- Other grade 3 in-field toxicities attributable to radiation that do not resolve to Grade 2 or less within 4 days with medical management
- Delays of more than one week in completing radiation treatment due to toxicity (cumulative duration of delay over the course of the entire treatment).

Additionally, toxicities attributable to radiation after the DLT assessment period (3 weeks after radiation is completed) will be followed and scored but will not be used for escalation with the following exception. If Grade ≥ 4 late bowel or bladder injury (late toxicity is defined as occurring >90 days after completion of radiotherapy) is observed in 2 patients in any Dose level group, dose escalation will be terminated and the dose below that dose level in which the toxicity was observed will be considered the MTD. Early and late toxicities used for assessment of DLTs should be attributable (possible, probable or definite) to radiation. Sexual and erectile dysfunction as a result of radiation will not be considered a DLT. Note that MTD will be determined for each Group separately.

Dose-limiting toxicities are defined as per section **3.1.1**.

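### Under section 8.4.4, Grade ≥4 bowel or bladder injury first occurring on days 22 to 90 after radiation counts toward neither the DLT rule nor the late stopping rule, while section 3.1.1 can be read as counting it

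*Combined protocol and SAP*

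**What the plan says.** Section 3.1.1 sets the DLT period as treatment plus the next three weeks. The first criterion is "Grade 3 rectal, small bowel, or urinary toxicity that does not resolve to Grade 2 or less within 4 days with appropriate medical management". The second applies the same four-day test to other in-field Grade 3 toxicity attributable to radiation. The third is "Delays of more than one week in completing radiation treatment due to toxicity", summed over the course. Section 8.4.4 repeats all three.

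Both sections then say that later toxicity is tracked but does not drive escalation, with one exception. If two patients at a dose level have Grade ≥4 late bowel or bladder injury, escalation ends and the level below becomes the MTD. Section 3.1.1 attaches this exception to "toxicities that occur more than 3 weeks after completion of treatment and during the 24 month follow up period" and does not say when late begins. Section 8.4.4 adds that "late toxicity is defined as occurring >90 days after completion of radiotherapy". The background in 1.2.1 uses the same 90-day boundary.

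Section 8.4.1 states: "The dose level on which 2 patients experience unacceptable toxicity is considered to have exceeded the MTD". Section 3.7.1 lists "Unacceptable Toxicity as defined in section" 3.1.1 among the reasons for ending protocol therapy.

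On replacement, 3.1.2 says: "If a patient did not experience DLT and did not finish treatment, he will not be evaluable for toxicity and will be replaced". Sections 8.3 and 8.3.1 exclude from the toxicity set anyone removed for a reason other than a DLT. Their only example is an illness unrelated to radiation.

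**The concern.** The MTD is the only primary endpoint, and in a 3+3 design it rests on counts of one or two patients. One uncounted DLT turns 1/3 into 0/3, so the arm escalates without the three extra patients. It can also turn 2/6 into 1/6, so the arm escalates instead of stopping.

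The main difficulty is the start of the late rule. An injury on day 100 can end escalation, but under 8.4.4 the same injury on day 40 cannot. An analyst working from 8.4.4 and an investigator working from 3.1.1 could declare different MTDs from the same patients.

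Two secondary gaps affect the same counts:

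- **Grade.** Neither DLT list says Grade 3 or higher, and neither names Grade 4, Grade 5 or death.
- **Replacement.** A patient who stops because of radiation toxicity short of a listed DLT is dropped from the denominator and replaced.

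**Working it through.** **The plan's own figures.** The maximum is 2 arms × (3 levels × 6 + 6 expansion) = 48, and the minimum is 2 arms × 2 = 4. Both match 8.2. One dose level in one arm therefore holds 3 or 6 patients during escalation, and up to 6 + 6 = 12 if it becomes the MTD and is expanded.

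**Timeline after the end of radiation.**

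| Days | 3.1.1 | 8.4.4 |
|---|---|---|
| 0–21 | DLT rule | DLT rule |
| 22–90 | Late not defined; the exception reads naturally as applying | Neither rule |
| 91 to month 24 | Two-patient rule | Two-patient rule |

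The uncovered interval is 90 − 21 = 69 days.

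**Does other text close the gap?** Section 8.4.1 uses the term unacceptable toxicity, but 3.7.1 defines that by pointing back to 3.1.1, so it adds no criterion. Section 8.4.4 ends by referring to 3.1.1 for the definition of DLTs. That sentence does not mention the late rule and does not clearly override the 90-day definition just above it.

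**Would the data exist?** Yes. The study calendar has adverse events assessed at 1 and 3 months. Section 6.1 requires all events through at least 30 days, after which "only adverse events which are serious and related to the study intervention need to be recorded". A radiation-related Grade ≥4 bowel or bladder injury would ordinarily meet that condition.

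**Size of the main gap.** The documents give no rate r for Grade ≥4 bowel or bladder injury on days 22–90, so r is assumed. Patients are taken as independent and the count as made within one arm. With n treated at a level:

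P(2 or more) = 1 − (1 − r)^n − n·r·(1 − r)^(n−1)

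For r = 0.05 and n = 6 this is 1 − 0.7351 − 0.2321 = 0.033.

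| Assumed r | n = 3 | n = 6 | n = 12 |
|---|---|---|---|
| 1% | <0.001 | 0.001 | 0.006 |
| 2.5% | 0.002 | 0.009 | 0.035 |
| 5% | 0.007 | 0.033 | 0.118 |
| 10% | 0.028 | 0.114 | 0.341 |

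The n = 12 column includes the optional expansion, which is entered only after the MTD is identified. It bears on revising the MTD and not on escalation.

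For scale, 1.2.1 cites acute Grade 3 or higher rates under standard treatment of 2% GU and 0.5% GI. That is about 2.5% if no patient has both, and acute there means during radiation or within 90 days. The 5% and 10% rows therefore assume a Grade ≥4 rate of 2 and 4 times that Grade ≥3 rate.

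**Secondary points.** On a strict reading, a Grade 4 event that falls to Grade 2 or less within 4 days without more than a week's delay meets no DLT item, and neither does a Grade 5 event. The documents give no rate for these events or for toxicity-related stops. The chance that a 3+3 escalates past a level with DLT probability p is (1 − p)^3 + 3p(1 − p)^5. At p = 0.025 this is 0.993 with every event counted, so missed events could add at most 1 − 0.993 = 0.007. That ceiling would hold for any counting defect; it shows only that little is at stake at that rate.

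**The case against.** The strongest reply is that the intended rules can be recovered from the text.

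- **Late rule.** In 3.1.1 the exception qualifies a window running from 3 weeks to 24 months, so it naturally covers all of it, and 8.4.4 closes by deferring to 3.1.1. This supports the likely intent. However, the deferral names DLT definitions only, and the explicit 90-day definition remains in 8.4.4, so the inconsistency stands.
- **Grade.** The test is failure to reach Grade 2 or less. If Grade 3 is taken as a floor, a persistent Grade 4 or a death fails it. Grade ≥3 was probably intended. What remains is the brief Grade 4 event, and the fact that the same section writes Grade ≥4 for the late rule but plain Grade 3 here.
- **Replacement.** A man who stops permanently for toxicity never completes radiation, which can be read as a delay of more than a week. That is plausible, but no text says so.
- **Other safeguards.** Section 7.3 requires deaths within 30 days of a research intervention to be reported unless due to progressive disease, 7.4.1 has the team review toxicity, and 10.1 allows suspension for unacceptable risk. The first is mandatory but is not a DLT rule, and the other two leave the action to judgment.

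A reader might infer that the protocol deliberately ignores Grade 4 and 5 toxicity, that injuries on days 22–90 would go unseen, or that the MTD will be materially wrong. The documents support none of these. The wording is probably an oversight, the events are collected, and no rate is given that would make a wrong MTD likely.

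**Conclusion.** The point holds as a defect in wording that affects the sole primary endpoint. Under 8.4.4, two Grade ≥4 bowel or bladder injuries first occurring on days 22–90 trigger no escalation or stopping rule. Under the natural reading of 3.1.1 they do, and nothing in the text settles which governs. The Grade 3 wording and the replacement rule are lesser gaps with plausible benign readings.

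The expected effect is small at rates near those cited for standard treatment: about 0.009 for two or more such patients among 6 at an assumed 2.5%. It reaches 0.114 among 6 only at an assumed 10%. Rates under these regimens are unknown, and 1.2.2 describes the approach as substantially more hypofractionated than those studied before in this setting, so higher values cannot be excluded. The inconsistency itself does not depend on any assumed rate. It should be corrected because the correction is cheap and the counts are small.

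**What to change.** 1. In 3.1.1 and 8.4.4, apply the two-patient Grade ≥4 bowel or bladder rule to radiation-attributable events from more than 3 weeks after radiation through month 24. Remove the 90-day limit from that rule.
2. In both DLT lists, change Grade 3 to Grade ≥3, limit the item on other in-field toxicity to non-hematologic events (5.1.1 describes treatment-related lymphopenia), and state that a radiation-attributable Grade 5 event is a DLT. Keep the sexual and erectile exclusion. Counting a brief Grade 4 rectal, small bowel, urinary or other in-field non-hematologic event whatever its duration is recommended, but that is a design choice for the sponsor.
3. In 3.1.2, 8.3 and 8.3.1, limit replacement to patients who stop for reasons unrelated to radiation toxicity, and state that a permanent stop because of radiation toxicity meets the delay criterion.

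The cost is a wording amendment to five sections (3.1.1, 3.1.2, 8.3, 8.3.1, 8.4.4). The maximum of 48 patients does not change. Slightly more events may count toward stopping, and patients already treated need a re-check against their recorded adverse events.
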